2.3. Methods of Analysis

2.3.1. General Analysis Specifications

Unless specified otherwise, summary will be shown by randomized/registered treatment arm with descriptive statistics. The dates used in the derivations are those obtained after applying the rules specified in Section 2.1.2.

The intensity (severity) of adverse events and the grade of abnormal laboratory results will be assessed using National Cancer Institute Common Terminology Criteria for Adverse Events (NCI CTCAE) Version 4.0.

2.3.2. Demographics and Baseline Characteristics

All demographic and baseline characteristic variables will be summarized for the ITT population.

The stratification factors used during randomization (palpation, platelet count) will be tabulated.

Demographic and baseline characteristic data will be summarized, including sex, age (years), race, ECOG performance status, region, weight (kg), and height (cm).

Two panels of baseline clinical laboratory tests specified in Section 2.3.9.3 will be summarized: hematology, and serum chemistry. Frequencies of CTC grade at baseline will be reported.

Diagnosis will be summarized by type of Myelofibrosis (PMF, ET-MF[PET], PV-MF[PPV]), risk category (Intermediate-2, High-Risk), relapse criteria (Yes, No for C1-C4), relapse type (5-10 cm with 100% increase, >10 cm with 50% increase, new spleen), age at diagnosis, and time since initial diagnosis (month).

Hepatitis serology test at baseline will be summarized by test type and results.

Myelofibrosis Symptoms at baseline will be summarized using descriptive statistics.

Transfusion history will be summarized by transfusion in last 12 week (yes, no), total transfusion unit, number of transfusion, and transfusion dependency (yes, no)

Medical history will be summarized.

In addition, summaries of bone marrow findings at baseline will be provided.

2.3.3. Prior Systemic and Subsequent Anti-cancer Treatment

Frequency distribution (n and percent) of subjects receiving prior systemic treatment before randomization will be presented, along with medication terms (according to the WHO drug dictionary and ATC). Subsequent anticancer treatment will be summarized in similar fashion as prior systematic treatment.

2.3.4. Prior and Subsequent Radiotherapy

Frequency distribution (n and percent) of subjects receiving radiotherapy before randomization will be provided, along with radiotherapy sites. Subsequent radiotherapy treatment will be summarized in a similar fashion as prior radiotherapy treatment.

2.3.5. Subject Disposition

Disposition information will be summarized for the ITT population.

Subject enrollment will be summarized by country and investigator.

The number of subjects enrolled, treated, still on treatment, and discontinuing study treatment with reasons will be reported for ITT population at the end of treatment.

The number of subjects enrolled, treated, still on study, discontinuing study with reasons will be reported for ITT population at the end of study.

Time on treatment (in weeks) and time on study (in months) will be summarized. Time on study is defined the same way as overall survival (OS) with reversed censoring, i.e., subjects who died will be censored. Based on this definition, time on study is the same as length of follow up. The Kaplan-Meier method will be used to estimate the median time on study.

2.3.6. Extent of Exposure

All exposure summaries are to be presented for the treated analysis set.

The number of treatment cycles received will be summarized along with the duration of treatment exposure, total doses (mg/kg), total number of infusions received, dose interval, dose intensity, and relative dose intensity for study drug. In addition, total doses (mg/kg), dose intensity, and relative dose intensity for study drug will be further summarized by cycle. For study drug, the following summaries are to be reported: number of subjects dosed, number of subjects with dose reduced, dose discontinued, dose withheld, and any change in dosing (reduced, withheld, dose delayed).

Reasons for dose changes will be summarized by cycle, as well as across the study, for each of the following changes: cycle delay (≥ 4 days), dose reduction, and dose withholding.

For each type of dose changes mentioned above, adverse events leading to changes in doses of study treatment will be summarized.

2.3.7. Concomitant Medications

Concomitant therapies other than antineoplastic agents or other systemic therapies for MF, post ET-MF, and post PV-MF after randomization will be classified by preferred WHO Anatomical Therapeutic Chemical (ATC) and summarized by therapeutic class and pharmacological class. Separate analyses will be performed for concomitant medications started during treatment and for all concomitant medications use (including baseline use).

2.3.8. Efficacy

2.3.8.1. Analysis Specifications

2.3.8.1.1. Level of Significance

All tests will be 1-sided. The primary efficacy endpoint will be tested at the overall significance level of 0.025. No treatment arm comparison will be performed between the two treatment arms.

2.3.8.1.2. Spleen Assessment by Independent Review Committee (IRC)

MRI of the abdomen will be performed to assess spleen volume. The scans will be sent to and read by an Independent Review committee (IRC). The radiological images will be collected at baseline and every 12 weeks up to week 48 and then every 24 weeks and at time of CR/PR.

The radiologists will be blinded to treatment assignment.

2.3.8.1.3. Modified Myelofibrosis Symptom Assessment Form (modified MFSAF v2.0)

Subjects will use a hand-held electronic device to record answers to queries regarding MF symptoms. Questions on these symptoms are from the modified MFSAF v2.0 questionnaire and will be completed by subjects each night beginning at Day -7 (prior to randomization), and continuing to the Week 48 visit. Symptoms will be assessed including 1) night sweats, 2) itchiness, 3) abdominal discomfort, 4) pain under ribs on left side, 5) early satiety, 6) bone or muscle pain, and 7) inactivity. Scoring is from 0 (absent/as good as it can be) to 10 (worst imaginable/as bad as it can be) for each item. The total symptom score (TSS) will be calculated as the 7-day average of daily TSS, which is the summation of 6 individual symptom scores (night sweats, itchiness, abdominal discomfort, pain under ribs on left side, early satiety, and bone or muscle pain).

2.3.8.1.4. Response Assessment Criteria

All assessments will be done according to the modified myeloproliferative neoplasms research and treatment (IWG-MRT) response criteria defined in the protocol ([Table 1](#), [Table 2](#)).

Table 1: Response Categories

Response Category	Required Criteria
	For all response categories, benefit must last for ≥ 12 weeks to qualify as a response
Clinical Improvement (CI)	The achievement of anemia, spleen or symptoms response without progressive disease or increase in severity of anemia, thrombocytopenia, or neutropenia ^a
Anemia Response	Subjects not transfusion dependent at baseline: a ≥ 20 g/dL increase in Hb ^b Transfusion dependent subjects at baseline: becoming transfusion independent. Transfusion independence is defined as absence of any pRBC transfusions for at least 12 “rolling” weeks ^b
Spleen Response	A baseline splenomegaly that is palpable at 5-10 cm, below the LCM, becomes not palpable or A baseline splenomegaly that is palpable at >10 cm, below the LCM, decreases by $\geq 50\%$ A spleen response requires confirmation by MRI showing $\geq 35\%$ spleen volume reduction
Symptoms Response	A $\geq 50\%$ reduction in the modified MFSAF v2.0 TSS ^c
Progressive Disease	Splenomegaly requires MRI showing a $\geq 25\%$ increase in spleen volume from baseline or Appearance of a new splenomegaly that is palpable at least 5 cm below the LCM or A $\geq 100\%$ increase in palpable distance, below LCM, for baseline splenomegaly of 5-10 cm or A 50% increase in palpable distance, below LCM, for baseline splenomegaly of >10 cm or Leukemic transformation confirmed by a bone marrow blast count of $\geq 20\%$ or A peripheral blood blast content of $\geq 20\%$ associated with an absolute blast count of $\geq 1 \times 10^9/L$ that lasts for at least 2 weeks
Stable Disease	Belonging to none of the above listed response categories
Relapse	No longer meeting criteria for at least CI after achieving CR, PR, or CI, or Loss of anemia response persisting for at least 1 month or Loss of spleen response persisting for at least 1 month

^a Increase in severity of anemia constitutes the occurrence of new transfusion dependency or a ≥ 20 g/L decrease in hemoglobin level from pretreatment baseline that lasts for at least 12 weeks. Increase in severity of thrombocytopenia or neutropenia is defined as a 2-grade decline, from pretreatment baseline, in platelet count or absolute neutrophil count, according to the Common Terminology Criteria for Adverse Events (CTCAE) version 4.03. In addition, assignment to CI requires a minimum platelet count of $\geq 25,000 \times 10^9/L$ and absolute neutrophil count of $\geq 0.5 \times 10^9/L$.

^b Transfusion dependency before study enrollment is defined as transfusions of at least 6 units of packed red blood cells (PRBC), in the 12 weeks prior to study enrollment, for a hemoglobin level of <85 g/L, in the absence of bleeding or treatment-induced anemia. In addition, the most recent transfusion episode must have occurred in the 28 days prior to study enrollment. Response in transfusion-dependent patients requires absence of any PRBC transfusions during any consecutive “rolling” 12-week interval during the treatment phase, capped by a hemoglobin level of ≥ 85 g/L.

^c Symptoms are evaluated by the modified MFSAF v2.0 TSS. The modified MFSAF v2.0 TSS is assessed by the patients themselves and this includes night sweats, itchiness, abdominal discomfort, pain under ribs on left side, early satiety, bone or muscle pain, and inactivity. Scoring is from 0 (absent/as good as it can be) to 10 (worst imaginable/as bad as it can be) for each item. The modified MFSAF v2.0 TSS is the summation of all the individual scores, excluding inactivity (0-60 scale). Symptoms response requires $\geq 50\%$ reduction in the modified MFSAF v2.0 TSS

For the response categories for CR and PR, the modified 2013 IWG-MRT criteria defined in the protocol will be used (Table 2).

Table 2: Remission Parameters

Parameters	Complete Remission (CR)	Partial Remission (PR) (Scenario 1)	Partial Remission (PR) (Scenario 2)
For all response categories, benefit must last for >12 weeks to qualify as a response			
Bone marrow	Normocellular <5% blasts ≤ Grade 1 fibrosis	Normocellular <5% blasts ≤ Grade 1 fibrosis	Not meeting bone marrow remission criteria
Immature myeloid cells in PB	<2%	<2%	<2%
Hemoglobin	10 g/dL – ULN	8.5 – <10 g/dL – ULN	10 g/dL – ULN
Neutrophils	1 x 10 ⁹ /L – ULN	1 x 10 ⁹ /L – ULN	1 x 10 ⁹ /L – ULN
Platelets	100 x 10 ⁹ /L – ULN	50 - <100 x 10 ⁹ /L – ULN	100 x 10 ⁹ /L – ULN
Spleen	Not palpable and ≤350ml volume	≥35% splenic volumetric reduction by MRI or not palpable	≥35% splenic volumetric reduction by MRI or not palpable
EMH	No non-hepato-splenic EMH	No non-hepato-splenic EMH	No non-hepato-splenic EMH
Symptoms	>70% improvement in symptom score per modified MFSAF v2.0 TSS	>50% improvement in symptom score per modified MFSAF v2.0 TSS	>50% improvement in symptom score per modified MFSAF v2.0 TSS

CR=complete remission; EMH=extramedullary hematopoiesis; MFSAF TSS= Modified Myelofibrosis Symptom Assessment Form Total Symptom Score; MRI=magnetic resonance imaging; PR=partial response; ULN=upper limit of normal

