6. DOSAGE AND ADMINISTRATION

Imetelstat Sodium (GRN163L) for Injection (imetelstat) is the investigational product in this study and will be provided by the sponsor. Imetelstat will be administered as a 2-hour IV infusion (\pm 10 minutes) at a constant rate using a programmable volumetric infusion pump. The baseline weight will be used to calculate the dose of imetelstat. The dose should be recalculated if there is a \geq 10% weight change from baseline. Subjects in Arm A will receive imetelstat 9.4 mg/kg every 3 weeks and subjects in Arm B will receive 4.7 mg/kg every 3 weeks. Subjects may receive treatment until disease progression or unacceptable toxicity. Study drug may be held for up to 21 days from the expected start date of the scheduled cycle; a hold >21 days must be reviewed and approved by the sponsor. Imetelstat should be discontinued permanently if it cannot be restarted within 21 days due to toxicity, unless approved by the sponsor. For treatment of hematologic toxicities, granulocyte colony stimulating factors (G-CSF) are permitted for neutropenia as well as blood transfusions for anemia or thrombocytopenia.

If a subject's status changes (including laboratory results or receipt of additional medical records) after screening but before the first dose of study drug is given such that he or she no longer meets all hematologic eligibility criteria, the decision to administer study drug on Cycle 1 Day 1 is at the discretion of the investigator provided that the subject does not meet any threshold for dose modification.

Dose Escalation Following Amendment 2

[figure not shown]
Beginning with Protocol Amendment 2, subjects in Arm B (4.7 mg/kg) may continue to receive their current dose of imetelstat or, at the discretion of the investigator, have their dose increased to 9.4 mg/kg. To be eligible for this dose escalation, a subject must meet study eligibility criteria for hematology laboratory values (inclusion criterion 8.1; ie, ANC \ge 1.5 x 10⁹/L; platelets \ge 75 x 10⁹/L) and biochemical laboratory values (inclusion criterion 9.1; ie, AST and ALT \le 2.5 x ULN, ALP \le 5 x ULN, serum creatinine \le 2 x ULN, total bilirubin \le 3 x ULN, direct bilirubin \le 2 x ULN). In addition, subjects may not meet any threshold for dose modification for hematologic toxicity

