Modified Myelofibrosis Symptom Assessment Form (MFSAF) Diary

Once eligibility has been confirmed via the Screening MF Symptom Form, subjects will be issued a hand-held electronic device to record answers to queries regarding MF symptoms. Questions on these symptoms are from the modified MFSAF v2.0 questionnaire²⁵ and will be completed by subjects each night beginning at Day -7, and continuing to the Week 48 visit. Symptoms will be assessed including night sweats, itchiness, abdominal discomfort, pain under ribs on left side, early satiety, bone or muscle pain, and inactivity. Scoring is from 0 (absent/as good as it can be) to 10 (worst imaginable/as bad as it can be) for each item. Detailed directions for the administration of the modified MFSAF v2.0 diary will be provided in a Reference Manual.

Myelofibrosis (MF) Symptom Recall Form

The MF Symptom Recall Form (Attachment 11) should be completed, starting after Week 48, at the time points specified in the Time and Events Schedule. The MF Symptom Recall Form is a paper questionnaire adapted from the modified MFSAF v2.0 diary, and includes a modified recall period of the average of the prior 7 days.

Efficacy Response Assessment

Response assessment for the response categories in Table 9 will be done per the modified 2013 IWG-MRT criteria. Assessment of response should include radiographic imaging, evaluation of blood and bone marrow (if applicable), and modified MFSAF v2.0 diary.

Table 9: Response Categories

Response Category	Required Criteria
	For all response categories, benefit must last for >12 weeks ^a to qualify as a response
Clinical Improvement (CI)	The achievement of anemia, spleen or symptoms response without progressive disease or increase in severity of anemia, thrombocytopenia, or neutropenia ^b
Anemia Response	Subjects with baseline Hb <10 g/dL but not meeting strict criteria for transfusion dependency: $a \ge 2$ g/dL increase in Hb ^c
	Transfusion dependent subjects at baseline: becoming transfusion independent. Transfusion independence is defined as absence of any pRBC transfusions for at least 12 "rolling" weeks ^c
Spleen Response	A baseline splenomegaly that is palpable at 5-10 cm, below the
	LCM, becomes not palpable or A baseline splenomegaly that is palpable at >10 cm, below the LCM, decreases by $\geq 50\%$
	A spleen response requires confirmation by MRI showing ≥35% SVR
Symptoms Response	A ≥50% reduction in the modified MFSAF v2.0 TSS ^d

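### The hemoglobin route to anemia response has no transfusion-free condition, so a 12-week rise sustained by red-cell transfusion would count

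*SAP*

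**What the plan says.** SAP Table 1 gives two routes to anemia response. For "Subjects not transfusion dependent at baseline" the criterion is a "20 g/dL increase in Hb". For dependent subjects it is becoming transfusion independent, and footnote b adds: "Response in transfusion-dependent patients requires absence of any PRBC transfusions" over a rolling 12-week interval, ending with hemoglobin of at least 85 g/L. The table head applies a duration rule to both routes ("For all response categories, benefit must last for" 12 weeks or more).

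Protocol 9.2.1, Table 9 has the same two routes. Its first covers "Subjects with baseline Hb <10 g/dL but not meeting strict criteria for transfusion dependency" and asks for a 2 g/dL rise, again with no transfusion condition.

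Both documents define dependency strictly. It takes six or more red-cell units in the 12 weeks before enrollment, given for hemoglobin below 8.5 g/dL, with the latest within 28 days, and with bleeding and treatment-induced anemia set aside. Protocol Section 6 permits "blood transfusions for anemia or thrombocytopenia", and Section 8 also allows blood product support. SAP 2.1.1 takes baseline as the last value on or before first dose. SAP 2.1.3 has no rule for hemoglobin measured after a transfusion.

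**The concern.** A subject who is not dependent is not necessarily untransfused. Someone given 1 to 5 units in the 12 weeks before enrollment is judged on hemoglobin alone, and may be transfused again on study. If transfusion holds the level up for 12 weeks, the rule credits supportive care as drug activity.

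Anemia response is a secondary endpoint. It is also one of three ways to qualify for CI, and so enters CRR (CR, PR or CI; SAP 2.3.8.3.1) and the duration analyses (SAP 2.3.8.3.2). SAP 1.2 says the development decision will draw on the totality of the data, including peripheral blood counts. There is no untreated arm against which such an error could show up.

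**Working it through.** The plan states no figure that can be reproduced here. The check is a reading of the two tables, a unit conversion and one illustration.

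**1. The tables side by side**

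| Element | Protocol Table 9 | SAP Table 1 |
|---|---|---|
| Who is on the Hb route | Not dependent, baseline Hb below 10 g/dL | Not dependent; no baseline Hb condition |
| Rise required | 2 g/dL | 20 g/dL as printed |
| Duration | 12 weeks | 12 weeks |
| Transfusion-free condition, Hb route | None | None |
| Transfusion-free condition, dependent route | 12 rolling weeks | 12 rolling weeks |

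The gap is in both documents. By dropping the baseline condition, the SAP widens the group judged on hemoglobin alone.

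**2. Units.** 20 g/dL × 10 = 200 g/L, and 2 g/dL × 10 = 20 g/L. The SAP footnotes give the other hemoglobin limits in g/L (20 and 85), so 20 g/L is evidently meant. Read literally, no subject could realistically meet the SAP row. What follows uses 2 g/dL.

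**3. Can transfusion alone hold the rise for 12 weeks without reaching six units?** The assumptions are not in the documents: own hemoglobin stays flat at baseline; each unit adds *u* = 0.7 to 1.5 g/dL; transfused cells decay with half-life *h* = 30 to 80 days. The transfused level after *t* days is level × 0.5^(*t*/*h*). Whole units are added whenever it is below 2 g/dL, from day 0 through day 84.

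Worked case, *u* = 1.0, *h* = 57, checked every 21 days. The retention factor is 0.5^(21/57) = 0.775.
- Day 0: 2 units, level 2.00.
- Day 21: 1.55, add 1, level 2.55.
- Day 42: 1.97, add 1, level 2.97.
- Day 63: 2.30, none needed.
- Day 84: 1.78, add 1.
- Total: 2 + 1 + 1 + 1 = 5 units.

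Units needed (top-up at 21-day visits / daily top-up):

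| *u* (g/dL) | *h* = 30 | *h* = 45 | *h* = 57 | *h* = 80 |
|---|---|---|---|---|
| 0.7 | 8 / 10 | 7 / 8 | 6 / 7 | 5 / 6 |
| 0.8 | 7 / 9 | 7 / 7 | 6 / 6 | 5 / 5 |
| 1.0 | 6 / 7 | 5 / 6 | 5 / 5 | 4 / 4 |
| 1.2 | 6 / 6 | 5 / 5 | 4 / 4 | 4 / 4 |
| 1.5 | 5 / 5 | 4 / 4 | 4 / 4 | 3 / 3 |

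The total is 5 or fewer in 12 of 20 cells with 21-day top-up and in 10 of 20 with daily top-up. These counts describe the grid; they are not probabilities. A partial rise of the subject's own would need fewer units, a fall more.

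**4. Passage into CI.** CI is blocked by progressive disease, new transfusion dependency, a 20 g/L hemoglobin fall lasting 12 weeks, or a two-grade platelet or neutrophil decline, and it has platelet and neutrophil floors. None of these blocks anemia response itself. For CI, new dependency is the guard that bears directly on transfusion, and it is incomplete. Five or fewer units do not reach it, and units given at 85 g/L or above do not count. The definition is also written for the period before enrollment and sets treatment-induced anemia aside, so how it applies on study is unclear.

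**The case against.** The best case against is that the route is harder to satisfy than it looks. The 12-week rule excludes a post-transfusion bump, so only a maintained plateau qualifies. The documents set no transfusion target that would create one. The only hemoglobin level they tie to transfusion is 8.5 g/dL; if units were given only below that level, a plateau 2 g/dL above baseline would need a baseline of about 8.5 − 2 = 6.5 g/dL or lower. At the unfavourable end of the table, 8 to 10 units are needed, which exceeds the dependency count. The CI exclusions remove further cases, and SAP 2.3.8.5 separately plans a 12-week transfusion-independence rate. All of this stands and makes the problem smaller. It does not close the gap: no rule in either document sets a transfused rise aside, and the transfusion-independence analysis is exploratory and leaves the anemia definition unchanged.

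A reader might infer more than the documents support:
- **That the error must favour the drug.** Baseline may itself follow a recent transfusion, which makes a 2 g/dL rise harder to reach.
- **That it distorts a comparison of doses.** No arm comparison is planned (SAP 2.3.8.1.1 and 2.3.8.2.2; Protocol 11.1).
- **That the earlier study shows how common it is.** The 42.1% with Grade 3 events in Protocol 1.1.5.3.1 refers to all 19 subjects of that study's Arm A, of whom 8 were transfusion dependent at baseline (1.1.5.1.1). It says nothing about transfusion in non-dependent subjects or about sustained rises.

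The criteria are presented as a modification of published ones, which are not available here. Whether the omission was introduced locally cannot be judged.

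**Conclusion.** The point holds as a gap in a secondary endpoint definition. As written, a hemoglobin rise kept up for 12 weeks by repeat transfusion is an anemia response. Unless a CI exclusion applies, it is also CI and CRR. This reading takes the intended threshold as 2 g/dL (20 g/L).

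The size cannot be stated. The number of non-dependent subjects transfused during a qualifying interval is not in the documents, and any inflation in percentage points would be invented. The unit counts show only that the case can arise below the six-unit threshold, and they rest on outside assumptions about rise per unit and cell survival. The net direction is uncertain because of the baseline effect. Spleen volume response and symptom response at Week 24, the co-primary endpoints, are unaffected. The change is worth making because it corrects a wrong classification at little cost.

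**What to change.** Make the change in SAP Table 1 and Protocol Table 9 together, since the SAP says it follows the protocol's criteria and changing one alone would create a conflict.

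1. Count a hemoglobin-based anemia response only if no red-cell transfusion was given during the 12-week response interval. Carry this through to CI, CRR and duration of response.
2. State how a baseline hemoglobin influenced by recent transfusion is handled.
3. Reconcile the SAP's 20 g/dL with the protocol's 2 g/dL (20 g/L).
4. Restore the protocol's baseline condition of hemoglobin below 10 g/dL in the SAP, or reconcile the two texts.

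This changes classification only, not transfusion practice. The data exist: transfusion status is assessed at each clinic visit (Protocol Time and Events Schedule, footnote c), and transfusions are recorded as concomitant therapy (Protocol Section 8). The cost is wording in two documents, some programming, and possibly a slightly lower anemia response rate.

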4.1. Inclusion Criteria

Each potential subject must satisfy all of the following criteria to be enrolled in the study.

- 1. \geq 18 years of age
- 2. Diagnosis of PMF according to the revised WHO criteria (Attachment 6); or PET-MF or PPV-MF according to the IWG-MRT criteria (Attachment 7). A report from the local laboratory for diagnosis of MF must be reviewed and approved by the sponsor.
- 3. DIPSS intermediate-2 or high risk MF (Attachment 8)
- 4. Measurable splenomegaly prior to study entry as demonstrated by:
 - palpable spleen measuring ≥5 cm below the left costal margin. The edge of the spleen should be measured in centimeters from the mid-clavicular line on the left side of the abdomen to the point of greatest splenic protrusion.

OR

- spleen volume of ≥ 450 cm³ measured by magnetic resonance imaging (MRI)
- 5. Active symptoms of MF as demonstrated by a symptom score of at least 5 points (on a 0 to 10 scale) on at least one of the symptoms or a score of 3 or greater on at least 2 of the following symptoms: night sweats, itchiness, abdominal discomfort, pain under ribs on left side, early satiety, bone or muscle pain, and inactivity.
- 6. Criterion modified per Amendment 1.
- 6.1 Documented progressive disease during or after JAK inhibitor therapy defined as worsening of splenomegaly-related abdominal pain at any time after the start of JAK inhibitor therapy, and

EITHER

- no reduction in spleen volume or size after 12 weeks of JAK inhibitor therapy
 OR
- worsening splenomegaly at any time after the start of JAK inhibitor therapy documented by:
 - increase in spleen volume from nadir by 25% measured by MRI or computed tomography (CT), or
 - increase in spleen size by palpation, CT, or ultrasound
 - o for splenomegaly of 5-10 cm at the start of JAK inhibitor treatment, at least 100% increase in palpable spleen size from nadir is required;

- o for splenomegaly of >10 cm at the start of JAK inhibitor treatment, at least 50% increase in palpable spleen size from nadir is required;
- o new splenomegaly must measure at least 5 cm.
- 7. ECOG performance status 0, 1 or 2 (Attachment 9)
- 8. Criterion modified per Amendment 1.
- 8.1 Hematology laboratory test values within the following limits:
 - Absolute neutrophil count (ANC) ≥1.5 x 10^9 /L (ie, ≥1,500/mm³) independent of growth factor support
 - Platelets $\geq 75 \times 10^9 / L$ (ie, $\geq 75,000 / mm^3$) independent of platelet transfusion support
- 9. Criterion modified per Amendment 1.

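### The PR spleen row accepts a non-palpable spleen without a baseline condition, so subjects who entered on MRI volume alone can meet it before treatment

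*SAP*

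**What the plan says.** Protocol 4.1, criterion 4, offers two routes to measurable splenomegaly, joined by OR: "palpable spleen measuring ≥5 cm below the left costal margin", or "spleen volume of ≥ 450 cm³ measured by magnetic resonance imaging (MRI"). The second route does not ask for a palpable spleen. Criterion 6.1 requires worsening splenomegaly-related abdominal pain together with a spleen finding. That finding can be volumetric, either "no reduction in spleen volume or size after 12 weeks of JAK inhibitor therapy" or a 25% volume increase from nadir on MRI or CT.

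Three spleen definitions then apply to response (SAP 2.3.8.1.4; protocol 9.2.1):

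- **CR:** "Not palpable and ≤350ml volume".
- **PR, Scenarios 1 and 2:** "≥35% splenic volumetric reduction by MRI or not palpable".
- **Spleen response (SAP Table 1, protocol Table 9):** a baseline spleen palpable at 5 cm or more must become non-palpable or, if above 10 cm, shrink by at least half. In addition, "A spleen response requires confirmation by MRI showing" at least 35% volume reduction.

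The PR wording is the same in the protocol and the SAP. No footnote or text in either document says how the palpation limb applies to a subject whose spleen could not be felt at baseline.

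**The concern.** A spleen that criterion 4 classes as measurable splenomegaly can satisfy the PR spleen row on the day of enrolment. The categories on either side are stricter: CR adds a volume ceiling, and the lower-ranked spleen response needs both a palpable baseline spleen and volumetric confirmation. PR carries neither safeguard.

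The interpretation of CR and PR is at stake. Protocol 3.2 uses them to capture depth of response and links them to possible disease modification. Protocol 1.1.3 reports no CR or PR with ruxolitinib and infers that the drug does not affect the underlying neoplastic process, so PRs here will be read against zero. PR Scenario 2 does not need marrow remission. From Amendment 2 subjects know their dose, so the symptom score that decides such a case may be open-label. Counts are likely to be low: in the earlier myelofibrosis study, 3 of 16 JAK-pretreated subjects had CR or PR (protocol 1.1.5.1.4). A single case is therefore visible in the result.

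**Working it through.** The plan states no figure that depends on this definition, so there is none to reproduce. The check is one of logic, plus arithmetic on the plan's own thresholds.

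**1. Can a non-palpable subject enrol?** Yes. Criterion 4 can be met on volume, and criterion 6.1 on volume plus pain.

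**2. What does each rule require of such a subject?** With baseline volume V, a 35% reduction means at most 0.65 × V, CR needs a reduction of 1 − 350/V, and MRI progression starts at 1.25 × V.

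| Baseline V (cm³) | PR row via palpation limb | PR row via volume limb | Reduction needed for CR | MRI progression from |
|---|---|---|---|---|
| 450 (entry floor) | met at 0% reduction | ≤ 292.5 | 1 − 350/450 = 22.2% | 562.5 |
| 500 | met at 0% reduction | ≤ 325 | 1 − 350/500 = 30.0% | 625 |
| 600 | met at 0% reduction | ≤ 390 | 1 − 350/600 = 41.7% | 750 |

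The palpation column holds only while the spleen stays non-palpable. If it becomes palpable, the subject needs the volume limb. If it becomes palpable at 5 cm or more, that is progression.

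**3. Is there an eligible subject for whom this decides PR?** Take a subject aged over 65 with constitutional symptoms, 1% circulating blasts, haemoglobin 10.5 g/dL and leukocytes not above 25 × 10⁹/L. DIPSS (protocol Attachment 8) is 1 + 1 + 1 + 0 + 0 = 3, intermediate-2. Add platelets 150 × 10⁹/L, neutrophils 3 × 10⁹/L, total immature cells below 2%, no extramedullary haematopoiesis outside liver and spleen, and a non-palpable spleen of 500 cm³. Every Scenario 2 row except symptoms is met at baseline. A symptom-score improvement above 50% for more than 12 weeks, with the spleen still non-palpable and below 625 cm³, then gives PR.

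**4. What would the same subject be without the palpation limb?** The PR symptom row (above 50%, more than 12 weeks) implies the Table 1 symptoms response (at least 50%, at least 12 weeks). Without progression or worsening cytopenia that is CI. The change is therefore from CI to PR. SAP 2.3.8.3.1 defines ORR as CR or PR and the clinical response rate (CRR) as CR, PR or CI. ORR gains one and CRR gains none.

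**5. Size.** The number non-palpable at baseline is not given. For illustration only, assume 2% to 20% of the 107 enrolled: 107 × 0.02 = 2.1 to 107 × 0.20 = 21.4 subjects. Assume also that 2% to 10% of these meet all other PR rows: 2.14 × 0.02 = 0.04 to 21.4 × 0.10 = 2.1 PRs whose spleen row was already satisfied at baseline. One such PR moves an arm's ORR by 100/67 = 1.5 to 100/39 = 2.6 points. Arm sizes are assumed: 39 is the smaller treated arm at the first interim review (protocol 3.2.1), and 67 is 107 − 40, which supposes that the other arm stayed at 40.

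**The case against.** **The profile is narrow.** This stands. With haemoglobin at 10 g/dL or above, intermediate-2 risk needs three of the four other DIPSS factors, while Scenario 2 also needs immature cells below 2% and neutrophils within normal limits. Subjects with haemoglobin below 10 must raise it or reach marrow remission. A reader might infer that PR on symptoms alone is easily reached; the other rows do not support that.

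**CRR is not inflated.** This also stands. A reader might infer that every response rate rises, but CRR already counts these subjects as CI. The exception is a subject barred from CI by a cytopenia rule but still inside the PR count ranges, for example haemoglobin falling from 12.5 to 10.4 g/dL for at least 12 weeks.

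**Remission describes an end state.** The count and extramedullary rows have no baseline condition either. That is a fair description of the table, but the spleen row differs: an enlarged spleen is an entry requirement, and the same table's CR column does not treat non-palpability alone as enough.

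**The header requires benefit lasting more than 12 weeks.** This hints at improvement, but benefit is not defined for the spleen row and cannot be programmed from that word.

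**Changing a protocol endpoint after two interim reviews has its own risk.** This stands, and is why both definitions should be shown. The separate summaries of spleen volume and length over time (SAP 2.3.8.5) help readers but do not change who is classed as PR.

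**Conclusion.** The gap is in the definition shared by the protocol and the SAP; it is not a discrepancy between them. Applied as written, it can turn a symptom-based CI into a remission with no spleen reduction. It reaches ORR, best overall response and duration of CR/PR. A reader might suspect the co-primary spleen endpoint or Table 1 spleen response as well, but both require at least 35% volume reduction and are untouched. Nor is the row met at any volume below the progression threshold regardless of palpation: continued non-palpability is needed.

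The effect is probably small and may be nil. The illustrative 0.04 to 2.1 cases rest wholly on assumed rates, and the 1.5 to 2.6 points per case on assumed arm sizes. It still merits correction, because few CRs and PRs are likely and they carry the disease-modification argument.

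**What to change.** In the SAP derivation of PR, both scenarios, apply the palpation limb only to subjects whose spleen was palpable at any length at baseline. Require at least 35% volume reduction by MRI for subjects non-palpable at baseline. A 5 cm baseline threshold should not be used: it would deny the palpation route to volume-entered subjects palpable at 1 to 4 cm whose spleen then becomes non-palpable.

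Report the number non-palpable at baseline by arm. List every PR that depends on the unrestricted palpation limb. Show ORR and duration of CR/PR under both the protocol definition as it stands and the restricted one. Because investigators assess response from the existing tables, the restricted version should be a programmed check against baseline palpation and MRI, leaving their recorded assessments unchanged.

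The cost is one extra condition and a second set of ORR and duration outputs, using data already collected at screening. ORR may be slightly lower under the restricted definition, and that derivation departs from the protocol table, which the SAP should state.
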